1.20 STUDY INTERVENTION COMPLIANCE

Since the drug or placebo will be applied intranasally by the physician at 2 visits, there is no need for compliance checks or verification of delivery.

1.21 CONCOMITANT THERAPY

Concomitant medications will not be restricted, except that we will ask subjects to avoid using other intranasal spray medications such as nasal saline, nasal decongestants or allergy sprays.

1.21.1 RESCUE MEDICINE

Not Applicable

STUDY INTERVENTION DISCONTINUATION AND PARTICIPANT DISCONTINUATION/WITHDRAWAL

Participants may withdraw voluntarily from the study or the PI may discontinue a participant from the study. In addition, participants may discontinue the study intervention, but remain in the study for follow-up, especially for safety and efficacy study endpoints (if applicable).

1.22 DISCONTINUATION OF STUDY INTERVENTION

If a patient notes a possible adverse effect, such as allergic reaction to study medication, we will discontinue study medication. Any new clinically relevant finding will be reported as an adverse event (AE). Because the outpatient course of study medication is only 6 days, we will not restart study medication in that short timeframe and instead will withdraw the patient from this study. Such patients will still be offered planned follow up and the planned outcome measures will still be collected.

The data to be collected at the time of study intervention discontinuation will include the following:

- Details of possible adverse event, and appropriate care as indicated (for example ER assessment).

1.23 PARTICIPANT DISCONTINUATION/WITHDRAWAL FROM THE STUDY

Participants are free to withdraw from participation in the study at any time upon request.

An investigator may discontinue or withdraw a participant from the study for the following reasons:

- If any clinical adverse event (AE), laboratory abnormality, or other medical condition or situation occurs such that continued participation in the study would not be in the best interest of the participant
- If the participant meets an exclusion criterion (either newly developed or not previously recognized) that precludes further study participation

The reason for participant discontinuation or withdrawal from the study will be recorded on the Case Report Form (CRF). Subjects who sign the informed consent form and are randomized but do not receive the study intervention may be replaced. Subjects who sign the informed consent form, and are randomized and receive the study intervention, and subsequently withdraw, or are withdrawn or discontinued from the study, will be replaced. Patients who do not complete the full course of study drug/placebo will be noted in the results tables, and they will not be included in the statistical analysis of outcome measures, since this is a simple comparison of SIT score between patients receiving 2 applications of drug versus placebo.

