1.31 POPULATIONS FOR ANALYSES

- Intention-to-Treat (ITT) Analysis Dataset (i.e., all randomized participants):

Placebo group (n=10)

Beclomethasone treated group (n=10)

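### Section 1.23 drops patients who do not complete both applications from the outcome analysis, which contradicts the all-randomized ITT set in section 1.31 and can bias the primary comparison

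*Combined protocol and SAP*

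**What the plan says.** Section 1.31 (Populations for Analyses) lists a single dataset, "Intention-to-Treat (ITT) Analysis Dataset (i.e., all randomized participants", with 10 in each group. No per-protocol or modified ITT set is named. Sections 1.32.1 to 1.32.3 give no missing-data method or sensitivity analysis.

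Section 1.23 (Participant Discontinuation/Withdrawal) contains two separate rules.

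- **Exclusion:** those who stop before finishing the course are listed in the tables, but "they will not be included in the statistical analysis of outcome measures". The reason given is "since this is a simple comparison of SIT score between patients receiving 2 applications of drug versus placebo".
- **Replacement:** patients who are treated "and subsequently withdraw, or are withdrawn or discontinued from the study, will be replaced". Those who are "randomized but do not receive the study intervention may be replaced", so replacement is optional for them.

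Section 1.22 (Discontinuation of Study Intervention) gives the one specific trigger for stopping: "If a patient notes a possible adverse effect, such as allergic reaction to study medication, we will discontinue study medication". It withdraws such patients but offers them follow-up, and says that "the planned outcome measures will still be collected".

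**The concern.** An ITT set is fixed at randomization. The section 1.23 set is fixed later, by whether the second application was given. Two analysts following this plan could report different primary results, and nothing in it says which result governs.

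Receiving the second application can depend on the arm. Section 1.7.1 lists local nasal irritation as a possible drug risk, section 1.22 stops medication for a possible adverse effect, and section 1.23 lets patients leave on request. If non-completion differs by arm and is related to later smell scores, the completers are no longer comparable groups. A result labelled ITT would then lack the protection that the label implies.

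**Working it through.** **1. The two sets compared.**

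| | Section 1.31 | Section 1.23 |
|---|---|---|
| Who is analysed | All randomized | Those who completed the course |
| When membership is fixed | At randomization | At the second application |
| Number | 10 per arm | 10 completers per arm only if every non-completer is replaced |

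If one of 20 randomized patients is replaced, 20 + 1 = 21 are randomized, and an all-randomized set of 10 + 10 is impossible.

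**2. The plan's own figure (section 1.30).** Inputs: SIT 24 versus 29, SD 4, alpha 0.05, power 0.8, t-test, 10 per arm.

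- Normal approximation, two-sided: n = 2 × [4 × (1.960 + 0.842) / 5]² = 10.05 per arm.
- Power at 10 per arm is 0.798 by the normal approximation and 0.753 by the noncentral t.

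The stated 10 is therefore reproduced approximately, and SD 4 is used below. (The section also calls the 4 a variance.)

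**3. Bias from dropping non-completers, with no true effect.** Assumptions that are not in the documents: k non-completers, all in the active arm, dropped and replaced so that 10 per arm are analysed. Non-completion is selected on a variable with correlation ρ to the SIT score.

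Expected bias = ρ × 4 × S / 10, where S is the absolute expected sum of the k lowest standard normal values. Two versions of replacement were run. Either replacements face the same selection (lowest k of 10 + k), or they are unselected (lowest k of 10, then k random additions).

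- k = 1, same selection, S = 1.59: ρ = 0.5 gives 0.5 × 4 × 1.59 / 10 = 0.32.
- k = 2, same selection, S = 2.75: ρ = 1 gives 4 × 2.75 / 10 = 1.10.
- k = 2, unselected, S = 2.54: ρ = 1 gives 4 × 2.54 / 10 = 1.02.

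Type I error comes from 200,000 simulated trials with a two-sided t-test at 5%:

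| Dropouts in active arm | ρ with outcome | Bias (SIT points) | Type I error |
|---|---|---|---|
| 1, 2 or 3 | 0 | 0 | 5% |
| 1 | 0.5 | +0.3 | about 5.5% |
| 2 | 0.5 | +0.5 | about 6.3% |
| 2 | −0.5 | −0.5 | about 6.3% |
| 1 | 1 (bound) | +0.6 | 7.1 to 7.5% |
| 2 | 1 (bound) | +1.0 to +1.1 | 10 to 11% |
| 3 | 1 (bound) | +1.3 to +1.5 | 12 to 16% |

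Replacement restores the count but does not remove the bias.

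**4. Cost of keeping non-completers.** With 10 analysed per arm, SD 4, and k retained active-arm patients who gain nothing, the expected difference is 5 × (10 − k) / 10. For k = 0, 1, 2 this is 5.0, 4.5 and 4.0 points. Two-sided t-test power (18 df) is 0.75, 0.66 and 0.56. If they keep half the benefit, power is 0.71 for k = 1 and 0.66 for k = 2.

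**The case against.** The strongest reply is about size. The larger figures need two or three dropouts, all in the active arm, who are exactly the poorest scorers. Section 1.30 allows for one lost subject per group. There are only two physician-applied doses. The second is due at about day 14 and the first post-baseline SIT at week 6, so no SIT result exists when completion is decided, and the trial is double-blind. Nothing in the documents links an adverse effect to poor smell recovery. Equal outcome-related dropout in both arms gives a mean bias of about zero, and a negative correlation reverses it. All of this stands, and the figures for perfect selection are bounds.

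Three stronger readings are tempting but unsupported.

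- A reader might infer that the plan will favour beclomethasone, or that its true error rate is about 11%. No non-completion rate or link to outcome is given, so neither follows.
- A reader might merge exclusion and replacement into one rule. The opening of the discontinuation section lets a patient stop the intervention and stay in the study, so that patient is excluded with no stated replacement. A patient who had both applications and then withdrew is replaced, but the exclusion sentence does not apply.
- A reader might assume that every non-completer's outcomes will be available. Section 1.22 promises collection only after discontinuation for an adverse effect, and not for voluntary withdrawal or loss to follow-up.

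The plan also offers some transparency: non-completers are noted in the results tables, and section 1.32.8 plans a table of individual data. That makes exclusions visible, but it does not say which analysis is primary.

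**Conclusion.** The contradiction is real whatever the dropout rate, and it determines who is in the primary analysis, so it must be fixed. The completers-only rule selects patients after randomization on something that treatment can affect, so it can bias the comparison. By how much, and in which direction, cannot be derived from the documents. Under the stated assumptions the effect runs from none (dropout unrelated to outcome), through about +0.3 points and 5.5% type I error (one dropout, correlation 0.5), to an extreme bound of about +1.0 to +1.1 points and 10 to 11% (two dropouts, perfect selection). None of these is a forecast.

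**What to change.** - Delete the sentence in section 1.23 that excludes non-completers from the outcome analysis.
- State that the primary analysis compares all randomized participants in their assigned arm, whatever the number of applications received, using every SIT collected. Report by arm how many have no post-baseline SIT, because these patients are randomized but contribute no outcome.
- Collect the week 6 and week 18 SIT and QOD from every non-completer who agrees to follow-up, not only those who stop for an adverse effect.
- Keep replaced patients in the ITT set and remove the fixed n=10 from section 1.31.
- Report the two-application completers as a supportive per-protocol analysis.
- Reconcile the 6-day course in section 1.22 with the Day 1 and day 14 applications in the synopsis, so that the full course has one meaning.

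The planned t-test can stay. The cost is protocol wording, follow-up of a few more patients at visits already scheduled, and the possible dilution shown above: t-test power of about 0.75 with no retained non-responder in the active arm, 0.66 with one and 0.56 with two.

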1.24 LOST TO FOLLOW-UP

A participant will be considered lost to follow-up if he or she fails to return for the 2 scheduled follow up Otolaryngology clinic visits and is unable to be contacted by the study site staff.

The following actions must be taken if a participant fails to return to the clinic for a required study visit:

- The site will attempt to contact the participant and reschedule the missed visit within 2 weeks and counsel the participant on the importance of maintaining the assigned visit schedule.
- Before a participant is deemed lost to follow-up, the investigator or designee will make every effort to regain contact with the participant (where possible, 3 telephone calls and, if necessary, a certified letter to the participant's last known mailing address or local equivalent methods). These contact attempts should be documented in the participant's medical record or study file.
- Should the participant continue to be unreachable, he or she will be considered to have withdrawn from the study with a primary reason of lost to follow-up.

SAFETY ASSESSMENTS

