1.30 SAMPLE SIZE DETERMINATION

Number of participants to enroll to have adequate power to test the key hypotheses for the study:

Placebo group: 10

Treatment group: 10

- Target study sample size: 10 subjects in each arm, 20 subjects total. Anticipated number to be screened in order to reach the target enrollment: 50 subjects
- *Outcome measure used for calculations: SIT score*
- *Test statistic: t-test*
- *Null and alternative hypotheses:*
 - Null hypothesis: There is no difference in SIT score with drug treatment or placebo.
 - Alternative hypothesis: NAC treatment results in improved SIT score.
- *Type I error rate (alpha): 0.05*
- *Power level: 0.8*
- *Assumed mean and variance:*
 - Placebo group, μ_1 : SIT=24 \pm 4
 - Treatment group, μ_2 : SIT=29 \pm 4

Reference: "Hypothesis Testing: Two-Sample Inference - Estimation of Sample Size and Power for Comparing Two Means" in Rosner, Bernard Fundamentals of Biostatistics, Belmont, Calif. : Duxbury Press, [1995].

SIT score of 24 is used for the placebo group because this is a score categorized as severe hyposmia (reduced olfaction). Based on published reports and our experience with long-COVID hyposmia subjects, we anticipate identifying and enrolling patients with a mean score of approximately 24 and a variance of approximately 4.

In terms of estimated possible improvement in SIT score with drug treatment, we have chosen an increase of 5 ± 4 points, because a jump of more than a few points on a repeat SIT test after one month is considered to be greater than just random chance³; (and [name], *personal communication*). There are no published data available for specifically measuring olfactory change following treatment with beclomethasone applied to the olfactory cleft topically for post-viral hyposia.

- *Anticipated impact of dropout rates, withdrawal, missing data, etc. on study power:* to compensate for such issues, we have increased our sample size by 1 subject per group.
- *Secondary endpoint:* We have included a secondary endpoint to measure quality of life via a validated questionnaire (QOD). We have no specific guides for mean or variance for the questionnaire in terms of possible beclomethasone or placebo treatment, so no calculations are possible. Nonetheless, a simple questionnaire poses no cost or risk, such that we see no reason to not collect these data.

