1.32.2 ANALYSIS OF THE PRIMARY EFFICACY ENDPOINT(S)

Primary endpoint is SIT score at 6 weeks and 18 weeks.

Placebo and drug-treated groups will be compared. SIT (mean \pm sd) will be compared via two-tailed t-test. SIT scores may range from 0-40, and normal scores are well-established. An assignment of normosmia, mild hyposmia, moderate hyposmia, severe hyposmia, anosmia, or probable malingering can be made based on SIT score.

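### Section 1.24 contradicts itself on a treated participant who is tested at week 6 and then cannot be reached, and separate t-tests at each visit make no use of that week-6 score at week 18

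*Combined protocol and SAP*

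**What the plan says.** **Status.** Section 1.24 opens by calling a participant lost when that person "fails to return for the 2 scheduled follow up Otolaryngology clinic visits" and, in addition, site staff cannot make contact. The procedure below it has a different trigger: "The following actions must be taken if a participant fails to return to the clinic for a required study visit". That is one visit. The site tries to rebook within 2 weeks, then telephones and writes. The last bullet reads: "Should the participant continue to be unreachable, he or she will be considered to have withdrawn from the study". Loss to follow-up is then the recorded reason.

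**Replacement and analysis set.** Section 1.23 says that participants who received study intervention and later withdraw will be replaced. It excludes from the outcome analysis only those who did not complete the course of drug or placebo. Section 1.31 defines the analysis set as intention-to-treat, all randomized, with 10 per group.

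**Analysis.** The primary endpoint is SIT at week 6 and at week 18. Section 1.32.2 states only that "SIT (mean \pm sd) will be compared via two-tailed t-test". Section 1.32.1 adds a nonparametric fallback for non-normal data. Neither gives a rule for a missing score. On dropout and missing data, 1.30 says "we have increased our sample size by 1 subject per group", and 1.33.7 provides for queries to the site.

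**The concern.** Take a participant who received both applications, gave a week-6 SIT and was unreachable by week 18. The two rules in 1.24 give opposite statuses. Nothing says whether the week-6 score is kept, or whether the participant, the replacement or both are counted. If this is left open, the choice may be made after results are seen.

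The second part is wider and covers reachable participants too. A t-test at week 18 needs a week-18 score. Anyone without one drops out of that test, and the week-6 score, which carries information about the missing value, goes unused. The two primary comparisons can then rest on different people.

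A comparison of attenders is safe when attendance is unrelated to outcome. Participants who noticed no gain by week 6 may be less inclined to return. If that happens more in one arm, the week-18 difference shifts. With 10 per arm, one participant is a tenth of the arm.

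**Working it through.** **Inputs from 1.30:** means 24 and 29, SD 4 (the text also calls the 4 a variance; the ± notation is read as an SD), alpha 0.05, power 0.80, 10 per arm. **Assumed, not in the documents:** week-6/week-18 correlation r = 0.7 (range 0.5 to 0.8 unless stated), one or two participants lost after week 6, bivariate normal scores, no replacement.

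**1. The plan's own figure.** The normal approximation gives n per arm = 2 × (1.96 + 0.84)² × 4² / 5² = 10.05, and power of 0.798 at 10 per arm. The planned two-tailed t-test has power 0.753 at 10 per arm. The baseline below is therefore 75%.

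**2. Random loss.** The expected difference stays 5.0. Power is 72.7% at 10 vs 9 and 70.2% at 9 vs 9. The cost is precision only.

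**3. The lowest week-6 placebo scorer misses week 18.** The expected minimum of 10 standard normal values is −1.539.
- Attenders' week-6 mean exceeds the full-arm mean by 1.539 × 4 / 9 = 0.684.
- The week-18 placebo mean rises by r × 0.684 = 0.7 × 0.684 = 0.48.
- The estimated difference is 5.00 − 0.48 = 4.52 (4.66 at r = 0.5; 4.45 at r = 0.8).
- Simulated t-test power is about 66% (68% at r = 0.5, 66% at r = 0.8).

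Of the fall from 75%, 75.3 − 72.7 = 2.6 points come simply from having one participant fewer.

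**4. The two lowest placebo scorers are lost.** The expected second-lowest value is −1.001, so the shift is 0.7 × 4 × (1.539 + 1.001) / 8 = 0.89. The estimate is 4.11, with simulated power of 56%.

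**5. No true effect, loss from the drug arm.** The same shifts become a spurious benefit of 0.48 (one lost) or 0.89 (two lost). Simulated type I error is 6.1% and 7.9%. Over r = 0.5 to 0.9 and one or two lost, it runs from 5.5% to 10.4%.

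**6. The same selection in both arms.** Losing the lowest scorer from each arm gives an estimate of 5.0, because the shifts cancel.

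**7. Using the week-6 score.** A likelihood estimate takes the attenders' week-18 mean plus b × (full-arm week-6 mean − attenders' week-6 mean), where b is the pooled within-arm slope. In step 3 the correction is about 0.7 × (−0.684) = −0.48 on the placebo mean, which restores 5.0. Simulation confirms bias of about 0.00 when loss depends on the week-6 score, against 0.33 to 1.13 for the attender comparison (r = 0.5 to 0.9, one or two lost). If loss depends on the unseen week-18 score, bias of 0.14 to 0.99 remains, against 0.66 to 1.27 for attenders.

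**The case against.** Several points limit the concern, and most of them stand.

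- **Who is affected by the status conflict.** A reader might infer that anyone who misses one SIT visit has no clear status. The text does not support that. Under 1.24, "The site will attempt to contact the participant and reschedule the missed visit within 2 weeks", and only a participant who stays unreachable after the calls and letter meets the conflict. One who is reached stays in the study with a missing score.
- **Whether bias is present.** A reader might infer that the week-18 result will be biased. The documents give no dropout rate or pattern, and participants are blinded, so discouragement could act equally in both arms. Bias needs loss that is related to outcome and unequal between arms.
- **The size is a worst case.** Step 3 always removes the single lowest scorer. If the lost placebo participant is drawn at random from the lower half, the estimate is 4.7 to 4.8 and power 68% to 70%. If the lost participant is replaced, the worst case becomes 4.5 to 4.7 and 69% to 71%. Replacement restores the count but does not remove the selection.
- **Omission is inferred.** The plan nowhere says that absent participants are dropped, and 1.31 names all randomized participants. But a t-test cannot use a score that does not exist, and no imputation is given, so omission is what the stated test implies.
- **The model is a choice.** A stated missing-score rule could also close the gap. The repeated-measures model is preferred because it uses data already collected and changes nothing in the arm differences when data are complete.

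**Conclusion.** The point holds in a limited form. Section 1.24 is inconsistent for a fully treated participant who is tested at week 6 and then unreachable, and 1.23 and 1.31 leave open whether that person, the replacement or both are counted. Separately, the stated t-tests make no use of a week-6 score when the week-18 score is missing, whether or not the participant can be reached.

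The resulting bias is conditional. With the plan's inputs, r = 0.7 and no replacement, the worst-case loss of one placebo participant costs about 0.5 of the planned 5 points and takes power from 75% to about 66%. Worst-case loss of one or two drug-arm participants under no effect adds 0.5 or 0.9 points and gives a type I error of about 6% or 8%. Random loss, or equal selection in both arms, gives essentially no bias. The documents support neither a claim that the trial will be biased nor a prediction of direction.

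**What to change.** - **1.24:** make the opening sentence and the bullets agree, and define missingness separately for the week-6 and week-18 visits.
- **1.32.2:** estimate the arm difference at each visit from one repeated-measures model on all observed SIT scores, with arm, visit and arm-by-visit terms, unstructured covariance and Kenward-Roger degrees of freedom. Align 1.32.1, including its nonparametric fallback.
- **1.23 and 1.31:** state that each attended SIT visit of the participant first randomized is kept, in line with the intention-to-treat set, even if a replacement is enrolled.
- **Reporting:** give the number tested by arm and visit, with a sensitivity analysis for missing week-18 scores whose imputed range is fixed in advance. Filling in the scale limits would tell little: on a 0–40 scale, one missing score in ten moves an arm mean across 40 / 10 = 4 points.

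The cost is wording and a little analysis time; no visits, data or participants are added. The drawback is that the model assumes missingness depends only on observed scores. If loss depends on the unseen week-18 score, it reduces the bias but does not remove it, so the sensitivity analysis is still needed. The changes should be settled before unblinding.
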